	Patients taking medications such as bisphosphonates, corticosteroids or any anti-inflammatory drug

If the patient meets the above criteria, the study coordinator will further discuss the details of the study and obtain consent from the patient and/or parent (if the patient is under the age of 18)- in a private manner and after all questions having been answered. Patients must be enrolled into the study prior to the routinely scheduled bonding of fixed appliances by their provider. Instructions will be given to the patient/parent prior to the first study visit (T0), including to not take any analgesic medications prior to the first appointment.

Study Procedures

I. Standardized Orthodontic Treatment Protocol

The orthodontic clinic treatment protocol will be standardized to minimize variability in the sequence of treatment. All subjects will be bonded with 0.022"X0.028" brackets passive self-ligating brackets with maximal band tension (MBT) prescription from 2nd premolar to 2nd premolar in both arches and bonded tubes on the 1st molars at the baseline (T0) visit. Each subject will have a 0.014" copper nickel titanium (NiTi) archwire placed at the initial visit. At T2, the next archwire in the sequence (0.014"X0.025" copper NiTi) will be placed.

Subjects will be seen at normally appointed visits every 4-6 weeks. The primary orthodontic provider will direct the alignment and leveling phase of treatment and proceed through the wire sequence as indicated. No specific procedure/timeframe will be assigned to placement of each archwire. Providers are expected to proceed to the next archwire when it can be placed comfortably based on the degree of alignment achieved.

In the event of bracket breakages, the subject is to be seen within 7 days to have the bracket rebonded, in standard care as well as the study. The primary orthodontic provider will reposition the bracket in the ideal position and continue with alignment using the study archwires. If the subject does not present with 7 days of the breakage, he/she will be disqualified from the study.

II. Randomization Procedures

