Once recruited to the study and after baseline measures are taken at T0 by the study coordinator, the randomization will be performed. Since study groups will be subdivided by gender, separate randomization will be performed for males and females. Block randomization will be used. Based on gender, 20 opaque envelopes will be generated containing the group allocation (10 for the vibration study group, 10 for the non-vibration control group). At the time of randomization, the

subject will choose an envelope and disclose the group assignment. For subjects allocated to the vibration group, the study coordinator will provide detailed instructions as to how to operate the appliance and will instruct those subjects to use it for 20 minutes per day.

Timetable of Study Assessments

Assessment/ Visit	Screen	Baseline T0	Visit T1	Visit T2	Visit T3
Week	2d-to -6w	0	5-6	10-12	15-17
Consent	X				
Inclusion Criteria/ Confirm	X	X			
Alginate Impression		X	X	X	X
Randomization *		X			
Braces applied /bonded		X			
Vibration Appliance instructions**		X			
Saliva Collection		X	X	X	X
Clinical Data		X	X	X	X
Periotest		X	X	X	X
Pain Diary*** & OHIP 14		X	X	X	X***
Model Analysis		X	X	X	X
Record Adverse Effects		X	X	X	X

*Randomization before bonding

**For vibration group only- SC initially provides device and manufacturer's instructions.

*** Diary provided @ Baseline & visit T1, T1 to be collected on next visit.

III. Data Collection Procedures (See Study Timetable)

On the day of bonding (T0), prior to the placement of any appliances, baseline unstimulated whole saliva will be collected and Periotest will be performed on selected teeth in the mandibular arch. In addition, alginate model impressions will be taken. These procedures will be described in more detail in the next sections. Once baseline measures have been taken, the PI will perform the randomization and notify the study coordinator as to which group the subject is assigned to ("vibration treatment" or "no vibration"). The patients allocated to the vibration treatment group

will be provided with the AcceleDent appliance and instructed to use the 20 minutes per day according to the manufacturer's instructions.

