The timing of visit activity is planned to coincide with normally scheduled clinic provider/patient visits. Typically, treatment for non-extraction cases last from 12-30 months in the Orthodontic clinic using fixed appliances. However, the subjects will only be evaluated during the first 6 months of their clinical appliance treatment for the study purpose and data. Providers will follow patients every 5-6 weeks and the study coordinator will ensure/confirm the patients for study appointments per Timetable, pg. 9. After completion of the observation and data collection phase (up to 17 weeks), the patients will continue to proceed with treatment as directed by the their primary orthodontic provider. Data collection will occur at normally scheduled visits with no additional appointments specific to the study.

In the event that the PI determines that a subject is not suited to continue in the study (eg. the subject shows consistent failure to keep appointed visits, consistent breakage of appliances, patient safety considerations, etc.) he/she will be withdrawn by the PI from the study and no further data will be collected. Specifically, poor compliance with attending appointments during the allotted time frame for each study visit will result in subjects being disqualified from the study. For example, the follow-up time frame for T1 is 5-6 weeks after T0 (baseline). Therefore if the patient misses an appointment and cannot or does not reschedule to attend his/her appoint during the allotted time from (by 6 weeks after T0), then he/she will be disqualified from the study. Also, in the event of bracket breakages (as stated earlier), the subject is to be seen within 7 days to have the bracket rebounded. The primary orthodontic provider will reposition the bracket in the ideal position and continue with alignment using the study archwires. If the subject does not present with 7 days of the breakage, he/she will be disqualified from the study.

The data collected to that point will be utilized in analyses. The patient's treatment will continue with the primary orthodontic provider consistent with the standard of care.

VI. Statistical/Data Analysis

Intra and inter-rater reliability of the irregularity measurements will be assessed using the T0 and T3 models evaluated by the two blinded evaluators one week apart for all patients. A Cronbach alpha analysis will be used to assess reliability of the measurements. A single calibrated evaluator

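### The withdrawal rule stops all data collection, so the scheduled adverse-effect record ends early even in subjects withdrawn for safety; it should continue after every early exit, in both arms

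*Combined protocol and SAP*

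**What the plan says.** The Timetable of Study Assessments has a row "Record Adverse Effects", marked at T0, T1, T2 and T3.

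Section V lets the principal investigator withdraw a subject judged unsuited to continue. Missed visits, repeated appliance breakage and safety are given as examples, and the sentence ends: "patient safety considerations, etc.) he/she will be withdrawn by the PI from the study and no further data will be collected".

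The same section then gives two specific exits. On visit windows: "poor compliance with attending appointments during the allotted time frame for each study visit will result in subjects being disqualified from the study". On bracket breakage, in the same words as section I (Standardized Orthodontic Treatment Protocol): "If the subject does not present with 7 days of the breakage, he/she will be disqualified from the study".

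On data already in hand: "The data collected to that point will be utilized in analyses".

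On contact after exit, the patient's "treatment will continue with the primary orthodontic provider consistent with the standard of care". For routine care in general, "Providers will follow patients every 5-6 weeks", and "Data collection will occur at normally scheduled visits with no additional appointments specific to the study".

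**The concern.** A subject taken out of a trial for safety is one whose later course matters for the harms record. Here the record stops at that point. Two things are lost: how an event already recorded develops or resolves, and any new event before week 17. The timetable also has no exit assessment. If a safety withdrawal falls between visits, no scheduled record captures the event that led to it.

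The Background section presents vibration as a physical approach that might avoid the side effects of drug methods. The adverse-effect record is the trial's direct check on that idea, and the subjects include minors aged 15-17. With 20 subjects per arm, each shortened record is 1/20 = 5% of an arm.

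**Working it through.** The plan states no figure for adverse effects, early exits or dropout, so there is nothing of its own to reproduce. The check has three steps: the scope of the rule, the scheduled records lost, and the routine visits still available.

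**Scope.** For withdrawal by the principal investigator, safety included, the stop is explicit. For the missed window and the late bracket repair, it follows from the order of the text: the general rule comes first, the two exits are introduced as particular cases of it, and the sentence limiting use to data gathered so far closes the passage. That is a reading, although the natural one. No other section makes an exception for adverse effects.

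**Records lost.** Post-baseline records are due at T1 (weeks 5-6), T2 (weeks 10-12) and T3 (weeks 15-17), so 3 per subject. If k have been taken before exit, 3 − k are absent.

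| Exit | k | Absent | Of which the visit itself was missed |
|---|---|---|---|
| Between T0 and T1 | 0 | 3 of 3 | 0 |
| At T1, after its record | 1 | 2 of 3 | 0 |
| At T2, after its record | 2 | 1 of 3 | 0 |
| Missed T1 window | 0 | 3 of 3 | 1 |
| Missed T2 window | 1 | 2 of 3 | 1 |

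In the last two rows the stop rule accounts for 2 and 1 of the absent records; the other is absent because the subject did not come.

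**Routine visits still due by week 17.** For exit in week w and visit interval d weeks, the number is the whole part of (17 − w)/d. Section V gives d = 5 to 6.

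- w = 5: 12/5 gives 2; 12/6 gives 2.
- w = 6: 11/5 gives 2; 11/6 gives 1.
- w = 10: 7/5 gives 1; 7/6 gives 1.
- w = 11: 6/5 gives 1; 6/6 gives 1.
- w = 12: 5/5 gives 1; 5/6 gives 0.

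So 1-2 routine visits remain after exit at T1, and 0-1 after exit at T2. Section I gives an interval of 4-6 weeks. At d = 4, w = 5 gives 12/4 = 3, so the ranges become 1-3 and 0-1.

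**What cannot be computed.** The documents give neither the number of subjects who will exit nor the split by arm. No total loss, and no size or direction of bias, follows from them.

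**The case against.** The strongest case against is that this matters little. Safety is not among the listed outcomes and section VI plans no analysis of adverse effects. Events recorded before exit still count, and no efficacy result, sample size or alpha depends on the rule. The counts above describe the timetable and do not show an effect. In a 40-subject pilot with up to 17 weeks of observation, continued recording adds one or two visits per subject at most at the section V interval. All of that is correct, and it is why the point is an inexpensive improvement and not a threat to the trial's results. It does not justify the rule, which gives a poorer harms record when it is followed exactly.

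The consent form was not available here and may describe follow-up after withdrawal. That is possible, but the protocol's own instruction would still be to stop.

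Many exits will be for non-attendance, and the Budget section ends payment to subjects dismissed for non-compliance. The record will be hardest to obtain in those subjects. This stands; the remedy is to show how many were followed, not to stop trying.

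Two further points stand as side issues. The plan does not say whether an exited subject goes on using the device, so later events would be easier to interpret if device use were noted. Exempting only adverse effects also leaves the stop on outcome data in place. If outcome collection is later extended past exit, the wording must be adapted.

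**Conclusion.** The concern holds. For subjects withdrawn by the principal investigator, including for safety, the protocol explicitly ends a record that its own timetable schedules through T3. For disqualified subjects the same follows on the natural reading. The size per subject is 2 of 3 post-baseline records after exit at T1 and 1 of 3 after exit at T2. With a missed window, 3 of 3 (T1) or 2 of 3 (T2) are absent, one of them through the missed visit itself. The effect on the trial's harms comparison is unknown because the number and split of exits are not given. No primary or secondary estimate changes. That the loss can be avoided rests on exited patients continuing routine visits, as section V expects, and on their consent to further recording.

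**What to change.** In section V, replace the clause that ends data collection with wording such as:

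> After withdrawal or disqualification, the only study data still collected are adverse effects. For every subject who exits, for any reason and in either arm, the reason and any event that led to it are recorded at exit. The study coordinator continues the adverse-effect record through week 17 at the routine visits the subject still attends, subject to consent (and parent permission at ages 15-17). If the next routine visit falls after week 17, events up to week 17 are asked about then. A subject who withdraws consent is not followed.

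In section VI, add:

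> Adverse effects and reasons for withdrawal or disqualification will be listed by arm, without a test. Events are marked as before or after exit, and the number of subjects followed for adverse effects to week 17 is shown for each arm.

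A note of whether the device was still in use would be a useful extra item in the listing.

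The cost is these sentences, a short listing, one sentence in the consent form with the matching parent permission, and slight extra recording for the subjects who exit. No extra appointment is needed. The record may stay incomplete where subjects stop attending; the number followed to week 17 makes that visible.

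### Randomised subjects who miss a visit window or delay a bracket repair are disqualified and, on the natural reading, no longer measured, although they stay in care at the same clinic

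*Combined protocol and SAP*

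**What the plan says.** All references are to the combined protocol and SAP.

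- **Timing of randomisation** (II. Randomization Procedures): "after baseline measures are taken at T0 by the study coordinator, the randomization will be performed". Every trigger below therefore acts on randomised subjects.
- **Visit windows** (V. Subject Participation): "poor compliance with attending appointments during the allotted time frame for each study visit will result in subjects being disqualified from the study". The worked example makes one T1 visit enough, if it is missed and not rescheduled by week 6.
- **Bracket breakage** (I. Standardized Orthodontic Treatment Protocol, repeated in V): "If the subject does not present with 7 days of the breakage, he/she will be disqualified from the study".
- **Withdrawal by the investigator** (V): a subject judged unsuited to continue is removed, in the words "he/she will be withdrawn by the PI from the study and no further data will be collected". The window rule follows at once, introduced as a specification of this, and the bracket rule is then added.
- **Use of data** (V): "The data collected to that point will be utilized in analyses".
- **Care afterwards** (V): the subject's "treatment will continue with the primary orthodontic provider consistent with the standard of care". Section V also says: "Data collection will occur at normally scheduled visits with no additional appointments specific to the study".
- **Non-compliance** (5) Budget): a participant who does not comply with the protocol is dismissed and receives no further payment.
- **Analysis** (VI. Statistical/Data Analysis): biomarkers are compared across the four gender-by-arm groups by a separate ANOVA at each visit. Irregularity is assessed as percentage change (Dental Model Analysis). Missing-data handling is not stated, and no sensitivity analysis for removed subjects is given.

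**The concern.** The randomised comparison at T1, T2 and T3 is protected only as far as the randomised subjects are still measured. These rules remove subjects for events after allocation, and the plan appears to stop measuring them by choice rather than by necessity. In a pilot of 40, with 10 subjects in each cell of the primary analysis, each removal takes 10% of a cell.

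Two things are at stake. Precision is lost whenever anyone is removed. Bias could follow as well, but only if removal is related to outcome and the selection differs between arms.

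**Working it through.** **Step 1. Does measurement stop on disqualification?** The explicit ban on further data is attached to withdrawal by the investigator. Two features extend it to the other rules: the window rule is presented as a specification of that withdrawal, and the paragraph ends by saying that data up to that point are used. This is the natural reading, not an explicit statement.

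**Step 2. Could these subjects still be measured?** In part. Their care continues with the primary provider, who works in the trial's clinic (Screening & Recruitment Procedures), and study data need no extra appointments. The in-window value of a missed visit is gone under any rule. An off-window sample and the later visits can still be obtained.

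**Step 3. Which analyses lose subjects?** The ANOVA at each visit after removal, and the percentage change in irregularity. The rater-reliability check on T0 and T3 models, planned for all patients, also has no T3 model for anyone removed earlier.

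**Step 4. Precision.** The plan gives no effect size, SD, power or dropout rate, so it has no figure to reproduce. A 10% or 20% loss is assumed, equal across cells, and results are in SD units.

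- Two arms, half-width = t(0.975, 2n-2) x sqrt(2/n):
  - n = 20: 2.024 x 0.316 = 0.640
  - n = 18: 2.032 x 0.333 = 0.677
  - n = 16: 2.042 x 0.354 = 0.722
- Two cells with the four-group pooled SD, half-width = t(0.975, 4n-4) x sqrt(2/n):
  - n = 10: 2.028 x 0.447 = 0.907
  - n = 9: 2.037 x 0.471 = 0.960
  - n = 8: 2.048 x 0.500 = 1.024
- Four-group ANOVA power at 0.05, noncentral F(3, 4n-4) with lambda = 4n x (d/2)^2, for an assumed arm difference d = 1 SD: 71.0%, 65.2% and 58.7% for n = 10, 9 and 8. For d = 0.8 SD: 49.9%, 44.9% and 39.7%.

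**Step 5. Bias and type I error, if loss were selective.** Simulation with 100,000 replicates, 20 v 20 normal outcomes (10 per gender cell) and no true effect. The k lowest subjects in an arm are removed on a score with correlation rho to outcome. Rank-sum test: two-sided 0.05, continuity-corrected normal approximation. The loss patterns and correlations are assumptions.

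| Removed (arm v arm) | rho | Bias (SD) | Rank-sum error | ANOVA error |
|---|---|---|---|---|
| 0 v 0 | - | 0 | 4.9% | 5.1% |
| 2 v 0 | 0.3 | 0.054 | 5.2% | 5.2% |
| 2 v 0 | 0.5 | 0.090 | 5.8% | 5.5% |
| 4 v 0 | 0.3 | 0.102 | 5.6% | 5.5% |
| 4 v 0 | 0.5 | 0.167 | 7.6% | 6.6% |
| 6 v 2 | 0.3 | 0.088 | 5.4% | 5.4% |
| 6 v 2 | 0.5 | 0.149 | 7.1% | 6.3% |
| 4 v 4 | 0.5 | 0 | 5.4% | 5.5% |

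**Step 6. Would baseline data reveal selection?** Only weakly. The half-width for removed v retained is t(0.975, 38) x sqrt(1/k + 1/(40-k)) = 1.07 SD for k = 4 and 0.80 SD for k = 8. With 4 removed from one arm and a baseline variable correlated 0.3-0.5 with the removal score, the comparison is significant in 13-28% of trials.

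**Step 7. Visit intervals against windows.** Section I gives routine visits every 4-6 weeks and section V every 5-6 weeks. The windows are weeks 5-6, 10-12 and 15-17. A steady 4-week rhythm gives weeks 4, 8 and 12, none in its matching window. A 5-week rhythm gives 5, 10 and 15, all inside. A 6-week rhythm gives 6, 12 and 18, so T3 is missed by a week.

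**The case against.** The strongest defence is scientific. The trial is a mechanistic pilot concerned with temporal change in biomarkers, and treatment is standardised to limit variability. A late saliva sample, or one from a subject whose bracket stayed off for more than 7 days, does not measure the intended exposure. That is a sound reason to keep an in-window, compliant analysis. It is not a reason to stop measuring.

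The second defence is that the harm is small. The cell half-width moves only from 0.91 to 0.96 SD at 10% loss, the loss rate is assumed, and there is no power target to miss. This stands as a limit on the size of the point. So do the plan's own mitigations: earlier data are kept, a visit rescheduled inside its window does not disqualify, and the coordinator confirms appointments against the Timetable. The last also means that the interval mismatch in Step 7 need not cause removals, although the passages still have to be reconciled.

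A reader might go further and infer that the comparison is biased towards one arm. The documents do not support that. The window and bracket rules are the same in both arms. The one arm-specific route is the Budget dismissal for non-compliance, because for the vibration arm only the coordinator "will instruct those subjects to use it for 20 minutes per day". Whether non-use of the device counts is not stated, and no monitoring of use is described, so this route is an inference.

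A reader might also infer that removed subjects are dropped from every analysis, or that the loss is wholly avoidable. The plan keeps data up to removal. And someone who could not reschedule inside the window has lost that in-window value for good; the documents do not say that such subjects will attend on time later.

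**Conclusion.** The concern holds in a limited form, and the plan should be changed. A stated rule, on its natural reading, gives up post-randomisation data that could partly be obtained at routine visits. The certain consequence of any removal is lost precision. Under the assumed 10-20% loss, the half-width rises from 0.91 to 0.96-1.02 SD between two cells and from 0.64 to 0.68-0.72 SD between arms.

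Those figures compare full with reduced numbers, so they are a ceiling on what continued measurement could restore. Bias is possible, not shown. It is zero if removal is unrelated to outcome or selects equally in both arms. If one arm alone lost 2-4 of its 20 subjects with correlation 0.3-0.5 to outcome, bias would be 0.05-0.17 SD and type I error about 5-7.6% (rank-sum) or 5.2-6.6% (ANOVA), a modest rise. Removal rates, correlations, one-sided loss and the 1 SD effect are all assumptions.

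**What to change.** Amend V. Subject Participation along these lines:

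> Disqualification does not end data collection. Saliva, Periotest, casts, diaries and OHIP-14 continue at routine visits for all randomised subjects unless consent is withdrawn or there is a safety reason. Completed diaries are always collected. The main analysis uses all randomised subjects with data, in their assigned arm. Actual weeks since bonding are recorded. Each off-window sample is assigned to the nearest scheduled visit, within a pre-stated limit on both sides. Samples beyond the upper limit for T3 are not used as T3. If two samples fall to one visit, the one closer to its window is used; ties go to the earlier. The planned tests are repeated on the in-window, compliant set. Removals and reasons are reported by arm.

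The limits follow from the windows. The boundary between T1 and T2 is (6 + 10)/2 = week 8, and between T2 and T3 it is (12 + 15)/2 = week 13.5. The half-gaps are thus 2 and 1.5 weeks, so a T3 limit of similar width is week 18.5 to 19. An open-ended T3 would be a mistake: irregularity and biomarkers change with time, so very late samples could add their own bias. The lower limit for T1 needs stating too.

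Also amend the ban on further data and the 17-week end of collection to match, and make the compensation sentence in 5) Budget consistent with retained visits. Reconcile the 4-6 week and 5-6 week intervals with the Timetable; no interval or clinical rule is proposed here.

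**Cost.** Wording, an ethics amendment and one rerun of the planned tests; no new model and no extra appointments. If 4-8 subjects were removed before T1, retaining them means at most 4 x 3 = 12 to 8 x 3 = 24 visits, or $1,200-2,400 at $100 each. That is within the $400 already offered per subject, and the samples are within the 40 x 4 = 160 implied by the schedule. The drawbacks are more spread in visit timing in the main analysis, which the in-window repeat will show, and a weaker incentive to attend on time.

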Two blinded clinical evaluators will assess the rate of alignment of the lower incisors for both groups. Analyses of dental casts will be done on the mandibular cast using a method based on Little's irregularity index. Little's irregularity index was developed to assess amount of anterior tooth displacement from canine to canine (see Cast Irregularity Data Collection Form). Contact displacement will be measured in millimeters around the arch from canine to canine. Irregularity will be measured on models from each of the four time points and be evaluated based on percentage change over the 6-month evaluation period.

Orthodontic Pain Assessment

Subjects will be given a pain diary on the baseline (T0), visits T1 & T2 to record the level of orthodontic pain each evening for the first 7 days after each study visit. The degree of pain will be assessed using a Visual Analog Scale (VAS) ranging from 1 (least pain) to 10 (highest pain)⁵⁴. In addition, patients will report if the pain is constant or only present on biting/chewing⁵⁵. The subjects will return the completed diary to the next visit to be collected by the study coordinator and kept in the study record.

Oral Health Quality of Life (OHQoL)

To assess the impact of the vibration appliance on the overall oral health quality of life of the subject, subjects will be given an Oral Health Impact Profile (OHIP-14) questionnaire⁵⁶. The OHIP-14 consists of 14 questions divided into specific dimensions including functional limitation, physical pain, psychological discomfort, physical disability, psychological and social disability and overall life handicap from orthodontic treatment with or without the vibration appliance. The OHIP-14 (exhibit below) will be administered at each study visit and the profile changes will be compared across time points in data analyses.

OHIP-14 Questionnaire:

Dimension	Question	Weight
Functional Limitation	Have you had trouble pronouncing any words because of problems with your teeth or mouth?	0.51
	Have you felt that your sense of taste has worsened because of problems with your teeth or mouth?	0.49
Physical Pain	Have you had painful aching in your mouth?	0.34
	Have you found it uncomfortable to eat any foods because of problems with your teeth or mouth?	0.66
Psychological Discomfort	Have you been self-conscious because of your teeth or mouth?	0.45

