	Have you felt tense because of problems with your teeth or mouth?	0.55
Physical Disability	Has your diet been unsatisfactory because of problems with your teeth or mouth?	0.52
	Have you had to interrupt meals because of problems with your teeth or mouth?	0.48
Psychological Disability	Have you found it difficult to relax because of problems with your teeth or mouth?	0.60
	Have you been a bit embarrassed because of problems with your teeth or mouth?	0.40
Social Disability	Have you been a bit irritable with other people because of problems with your teeth or mouth?	0.62
	Have you had difficulty doing your usual jobs because of problems with your teeth or mouth?	0.38
Handicap	Have you felt that life in general was less satisfying because of problems with your teeth or mouth?	0.59
	Have you been totally unable to function because of problems with your teeth or mouth?	0.41

Each question is answered on a 5-point scale:

0=never

1=hardly ever

2=occasionally

3=fairly often

4=very often

Individual scores are multiplied by the weights to give a subscale score for each category.

IV. Sample size and justification

Few studies exist evaluating salivary biomarkers during orthodontic tooth movement. Our primary outcome is changes in the expression of specific biomarkers of cellular activation and bone remodeling. No RCTs are currently available to predict treatment effects on biomarker expression. This study will serve as a pilot project with 40 patients total in 4 groups divided by gender and vibration/no-vibration treatment arms.

We estimate 600 patients in the target age range beginning orthodontic treatment at the University of Connecticut Orthodontic Clinic each year. We anticipate meeting our recruitment goal for this study.

V. Subject Participation

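### Cronbach alpha, the only reliability statistic named for the irregularity index, does not respond to a constant offset between evaluators or sessions, so such an offset could go undetected

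*Combined protocol and SAP*

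**What the plan says.** The Statistical/Data Analysis section (VI) sets the aim: "Intra and inter-rater reliability of the irregularity measurements will be assessed using the T0 and T3 models", with casts "evaluated by the two blinded evaluators one week apart for all patients". It then names one statistic: "A Cronbach alpha analysis will be used to assess reliability of the measurements". It gives no acceptance threshold or confidence interval, and it does not say whether T0 and T3 casts are analysed together or apart.

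Under Dental Model Analysis in section III, "Two blinded clinical evaluators will assess the rate of alignment of the lower incisors for both groups". The scale is absolute: "Contact displacement will be measured in millimeters around the arch from canine to canine". Casts from all four time points are read, and the result is to "be evaluated based on percentage change over the 6-month evaluation period". The plan does not say whether one evaluator's reading or the mean of the two enters the analysis.

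The documents name no absolute-agreement coefficient, paired mean difference, limits of agreement or measurement-error estimate for these readings. Outcome Assessments lists change in alignment as a secondary outcome.

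**The concern.** Rater reliability raises two questions: do the readings rank the casts alike, and do they give the same number of millimetres? Alpha answers only the first. A calibration difference between evaluators, or a drift between sessions a week apart, would appear mainly as a roughly constant offset, and alpha is built to ignore that.

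This matters because the baseline reading is the denominator of the percentage change, so the level of the readings enters the result directly. The irregularity index is also the only measure of alignment behind hypothesis 3 and Aim 3. By contrast, section VI gives all Periotest readings to a single calibrated evaluator. The casts have two evaluators and no stated calibration, so this reliability check is the only stated safeguard against disagreement between them. At stake is whether the reported percentage change can be trusted in absolute terms, and whether the published coefficient supports a claim of rater agreement.

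**Working it through.** **Inputs from the documents.** Two evaluators; 40 patients (section IV), hence at most 40 casts at each of T0 and T3; index in mm; analysis by percentage change. The plan states no reliability figure, so there is none to reproduce.

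**Assumed inputs.** T0 mean 8 mm, SD 2.5; T3 mean 2 mm, SD 1; random reading error SD 0.4 mm; one evaluator high by a constant b.

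**Formulas for two readings.** Let V be the true variance between casts and E the error variance (0.4² = 0.16).

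- Cronbach alpha = 2V / (2V + E). It is built from variances and covariances only, so b does not appear. It equals the consistency ICC for the mean of two readings.
- Absolute-agreement single-reading ICC = V / (V + E + b²/2), where b²/2 is the variance of two readings that lie b apart.

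**Results, T0 and T3 taken separately**

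| Casts | V | Alpha, any b | ICC, b = 0 | b = 0.5 | b = 1 | b = 2 mm |
|---|---|---|---|---|---|---|
| T0 | 6.25 | 12.5/12.66 = 0.987 | 0.975 | 0.956 | 0.904 | 0.743 |
| T3 | 1 | 2/2.16 = 0.926 | 0.862 | 0.778 | 0.602 | 0.316 |

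The b = 0 column shows that alpha exceeds single-reading reliability even without an offset: 0.987 against 0.975 at T0, and 0.926 against 0.862 at T3.

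**If T0 and T3 were pooled (not stated).** V = (6.25 + 1)/2 + (6/2)² = 12.625, and alpha = 25.25/25.41 = 0.994. The treatment change supplies 9 of the 12.625, so pooling raises alpha above either separate value.

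**If pooled, with the offset at T3 only.** Alpha = 2 × (1 − sum of reader variances / variance of the sum).

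- b = 1 mm: 2 × (1 − (12.785 + 10.035)/45.07) = 0.987.
- b = 2 mm: 2 × (1 − (12.785 + 7.785)/39.82) = 0.967.

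Alpha does move here, but only slightly.

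**Sensitivity to the assumptions.** With a 1 mm offset, between-patient SD of 1 to 3 mm and error SD of 0.2 to 0.5 mm, alpha runs from 0.89 to 0.998 and the absolute-agreement ICC from 0.57 to 0.94. With SD 1 mm and error SD 1 mm, alpha is 2/3 = 0.67, so it does respond to random error.

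**Effect on the endpoint, true fall 8 to 2 mm (75%)**

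- One reader, 1 mm high on both casts: (9 − 3)/9 = 66.7%.
- Mean of two readers, one of them 1 mm high: (8.5 − 2.5)/8.5 = 70.6%.
- Only the T3 reading 1 mm high (worst case considered): (8 − 3)/8 = 62.5%.

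**Effect on the contrast between arms.** Take true falls of 6.0 and 5.2 mm from 8 mm: 75% against 65%, a difference of 10.0 points. With both arms read 1 mm high on both casts, the difference is 0.8/9 = 8.9 points. With a T3-only offset in both arms it is 62.5 − 52.5 = 10.0 points.

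**Type I error.** I simulated no treatment effect with 20 patients per arm, a Wilcoxon rank sum test at 0.05 and 10,000 trials per scenario. Offsets were 1 and 2 mm, under four arrangements: same reader throughout, different readers at T0 and T3, readers assigned at random, and the mean of two readers. The rejection rate was 0.048 to 0.052 throughout.

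**The case against.** The strongest reply is that little harm can follow. Section IV describes a pilot: "This study will serve as a pilot project with 40 patients total in 4 groups". Alignment is secondary, the evaluators are blinded, and the test compares arms. The arithmetic and simulation above support this: an offset shared by both arms dilutes the contrast or leaves it alone, and does not produce false positives. That part stands, and it sets the severity.

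It is also fair that T0 and T3 casts "will be assessed using the T0 and T3 models evaluated by the two blinded evaluators", which most naturally means that both evaluators read both casts. A reader might infer that different evaluators read one patient's T0 and T3 casts, which is one way to reach the 62.5% figure. The plan does not say so. It leaves open whose reading is used and who reads T1 and T2.

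Two other strong readings are tempting. One is that alpha is bound to rate biased readings as excellent. The plan sets no threshold or grade, and alpha falls when random error is large. The other is that the plan pools T0 and T3. It does not say so, and the blindness to a constant offset holds either way. Finally, if the mean of the two evaluators is what gets analysed, a coefficient for the mean is the matching unit, so that part of the criticism depends on a rule that the plan does not give.

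None of this makes alpha a measure of agreement, and nothing else in the documents supplies one.

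**Conclusion.** The point holds as a minor one. That a constant offset leaves alpha unchanged is algebra and needs no assumption about this trial. The sizes do: every mean, SD, error and offset used here is assumed, and a 2 mm offset would equal the whole assumed T3 mean. On those assumptions a 1 mm offset moves a true 75% reduction by 4.4 points (mean of two readers), 8.3 points (one reader, both casts) or 12.5 points (T3 only). The first two leave alpha exactly as it was. The third lowers a pooled alpha only from 0.994 to 0.987.

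A reader might infer that the comparison of arms is invalid, or that a published alpha would be a false figure. The documents support neither. Alpha would be a correct consistency coefficient that says nothing about bias. The damage is to the reported percentage change and, through dilution, to the sensitivity of a secondary comparison.

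**What to change.** In section VI, replace Cronbach alpha with a two-way absolute-agreement single-reading ICC with 95% confidence interval. Compute it separately for T0 and T3 casts, and separately for inter- and intra-rater agreement. Add the mean paired difference and limits of agreement in mm, which show an offset directly. Under Dental Model Analysis, state that the same evaluator, or the mean of the two, supplies all four casts of a given patient.

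This is a cheap improvement. It uses readings already planned for all patients and changes wording only. The downside is that the reported reliability figure will be lower than alpha.
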